1 OVERVIEW

Congenital heart diseases (CHD) are the most common birth defects, occurring in nearly 1% of live births. Every year, an estimated 40,000 infants born in the U.S. suffer from CHD. Despite advances in surgical management, CHD requiring neonatal surgery is associated with poor outcomes; national registry data demonstrates post-operative major morbidity in 23% and 10% do not survive to hospital discharge.[1-4]

Poor outcomes after pediatric heart surgery are often attributable to a severe systemic inflammatory response to cardiopulmonary bypass (CPB).[5-8] CPB is necessary for most infant CHD surgeries. Therefore, to reduce the post-CPB inflammatory reaction, many surgeons administer pre-or intra-operative steroids.[9-15] Steroids have been shown to reduce inflammatory markers after neonatal heart surgery.[13, 16] However, steroids also have potential harmful effects including an increased risk of post-operative infection.[17] The recent SIRS trial evaluated the safety and efficacy of steroids after CPB in adults and demonstrated no beneficial effect of steroids but increased risk of post-CPB myocardial infarction and other major adverse events.[18, 19]

Adult trial results cannot be reliably extrapolated to infants because the neonatal response to CPB is markedly different to that seen in adults; infants demonstrate both a more pronounced inflammatory reaction and a different post-operative complication profile. For these reasons approximately 60% of congenital heart surgeons continue to administer perioperative steroids to infants undergoing heart surgery.[17] Yet this practice is not evidence based as no safety/efficacy trial has ever evaluated steroids in infants undergoing heart surgery with CPB. Several smaller steroid trials (all enrolling < 75 patients) have focused on surrogate outcome measures, but none have provided conclusive data.[16, 20]

The major barrier to performing a steroid trial in infants with CHD has been the high cost associated with trial conduct for these relatively rare defects. To overcome this barrier, we will use a novel approach leveraging existing registry infrastructure at CHD surgical sites that participate in the Society of Thoracic Surgeons Congenital Heart Surgery Database (STS-CHSD). Sites participating in the STS-CHSD collect data into their institutional databases using standardized case report forms (see Appendix A) so that the data can be exported to the STS-CHSD. These sites already employ data coordinating specialists to capture patient demographics, procedural variables, and post-operative outcomes (including a list of over 60 complication variables) using strict and consistent data element definitions. By leveraging these site-specific resources we project that we can reduce trial costs by >75%.

2 PROTOCOL SYNOPSIS

Protocol Title	ST eroids to RE duce S ystemic inflammation after infant heart S urgery (STRESS trial)
US IND Number	129266
Grant number	UO1TR001803-01
Product	Intravenous methylprednisolone
Objectives:	To determine the pharmacokinetics (PK)/pharmacodynamics (PD), safety and efficacy of methylprednisolone in infants undergoing planned heart surgery with cardiopulmonary bypass
Study Design:	This is a prospective, double blind, multi-center, placebo-controlled safety and efficacy study. Blood samples will be collected from a subset of enrolled study participants to evaluate single dose methylprednisolone PK/PD. After informed consent is obtained, participants will be randomized in a 1:1 fashion to intravenous methylprednisolone versus placebo. Study drug/placebo will be administered in the operating room at the time of initiation of cardiopulmonary bypass. Patients will be followed for primary and secondary outcomes for the duration of their hospitalization. Serious study drug-related adverse events will be collected for 7 days after the administration of study drug.
Rationale for study design	The study design will allow for evaluation of safety and efficacy to neonates receiving the drug. The proposed design will also allow for characterization of single dose methylprednisolone PK/PD.
Study Population:	Up to 1500 infants ages < 1 year undergoing planned heart surgery with cardiopulmonary bypass including a minimum of 400 neonates \leq 30 days at the time of surgery.
Number of Sites:	Up to 40
Duration of Subject Participation:	Until hospital discharge
Dose ranges to be studied	Intravenous methylprednisolone will be administered using a preservative free formulation. The dosage in this study will be 30 mg/kg
Dose Schedule:	Intraoperative methylprednisolone/placebo administered as a single IV dose into the cardiopulmonary bypass pump prime
Diagnosis and Main Criteria for Inclusion	Inclusion criteria: 1. Age < 1 year at the time of surgery 2. Undergoing planned heart surgery with CPB as part of standard clinical care. 3. Availability and willingness of the parent/legally authorized representative to provide written informed consent. Exclusion criteria: 1. < 37 weeks adjusted gestational age at time of surgery

	 Any oral or intravenous steroid treatment within two days of surgery Infection contraindicating steroid use Any patient receiving any of the following medications within 2 days of surgery: Amphoteracin B, aminoglutethimide, anticholesterases, warfarin, P450 3A4 inducers including (but not limited to) carbamazepine, phenobarbital, phenytoin, rifampin, bosentan and nafcillin or P450 3A4 inhibitors including (but not limited to) clarithromycin, voriconazole, itraconazole, ketoconazole, ciprofloxacin, diltiazem, fluconazole, erythromycin, azithromycin and verapamil. Preoperative mechanical circulatory support or active resuscitation at the time of randomization Previous enrollment in the STRESS trial
Estimated Start:	September 2017
Estimated Finish:	August 2021
Primary endpoints	 Primary efficacy and safety outcome measures will be compared between infants receiving any methylprednisolone and placebo. Primary endpoint - efficacy: The primary outcome measure will consist of a composite mortality, major morbidity and length of stay global rank endpoint with endpoints ranked according to severity. For this endpoint each randomized patient recieving study drug will be assigned a rank based upon their most-severe outcome.
Secondary endpoints	 Efficacy: Mortality including in-hospital mortality or mortality after hospital discharge but within 30 days of the last dose of study drug Death or major complication as defined by an outcome in one of the 6 highest global ranking categories Post-operative hospital length of stay Prevalence of prolonged (> 7 days) post-operative mechanical ventilation Occurrence of post-operative low cardiac output syndrome Safety: Occurence of any one or more of the following major post-operative infectious complications: Postprocedural infective endocarditis Pneumonia Sepsis Deep wound infection Mediastinitis Other post-operative complications will be collected from the start of study drug administration until hospital discharge. PK/PD/Biomarkers: Time to maximum concentration (T_{max}) Maximum concentration (C_{max}) Clearance (CL) Volume of distribution (Vd) Post-operative blood markers of inflammation

	Blood samples will be obtained from patients at various time points after the study drug infusion. PK parameters will be estimated by non-compartmental analysis using
DK/DD/Biomarkors	WinNonLin software. Study participants as well as enrolling centers will be given the
I K/I D/ Diomarkers.	opportunity to not participate in the PK/PD and/or Biomarker studies as these require
	needle sticks. Therefore it is expected that PK/PD and/or biomarker data will not be
	collected on every participant enrolled in the STRESS trial
	Safety/Efficacy: Safety and efficacy data will be collected at participating sites using their
	existing surgical databases (STS-CHSD). The majority of efficacy and safety outcomes
	represent data elements that sites are currently collecting for submission to the STS-CHSD.
	A separate clinical database will be used for expedited reporting of any study drug-related
Critoria for	serious adverse events. An independent Data Monitoring Board (DMC) will monitor the
Criteria lor	conduct of the trial for performance (e.g., recruitment, flow and quality control of data,
evaluation	adherence to the protocol) and patient safety. The DMC may review the data at any time.
	At any time and for any reason, the DMC may recommend to the sponsor that the trial be
	interrupted or discontinued.
	Pharmacokinetics: Methylprednisolone concentrations will be measured in plasma.
	Samples will be measured at a central lab using a validated bioanalytical assay.
Statistical	This protocol has sufficient enrollment to evaluate PK/PD, safety and efficacy of IV
Consideration:	methylprednisolone

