4.3.2 Secondary Endpoints (see section 11.2 for data element definitions)

Efficacy:

- Mortality including in-hospital mortality or mortality after hospital discharge but within 30 days of the last dose of study drug
- Death or major complication as defined by an outcome in one of the 6 highest global ranking categories
- Post-operative hospital length of stay
- Prevalence of prolonged (> 7 days) post-operative mechanical ventilation

• Occurrence of post-operative low cardiac output syndrome

Safety:

- Occurence of any one or more of the following STS-CHSD-defined major post-operative infectious complications:
 - Postprocedural infective endocarditis
 - o Pneumonia
 - o Sepsis
 - Deep wound infection
 - Mediastinitis
- Other post-operative complications will be collected from the start of study drug/placebo administration until hospital discharge.

PK/PD/Biomarkers:

- Time to maximum concentration (T_{max})
- Maximum concentration (C_{max})
- Clearance (CL)
- Volume of distribution (Vd)
- Post-operative blood markers of inflammation

PK/PD and Biomarker data will only be collected at select centers and in those patients whose parent/legally authorized representative have granted consent to blood draws. An opt in/out clause is included in the informed consent forms for study participants and centers will be allowed to participate in this part of the study if they prefer. Parent/legally authorized representative of participants may elect to participate in the PK/PD, the Biomarker studies or both. Time points for blood collection will be the same for both the PK/PD and biomarker studies. Biomarkers being collected represent blood markers of inflammation.

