6.5 PK/PD/Biomarker sampling procedures (select sites)

A limited PK/PD/Biomarker sampling scheme will be employed such that no more than 5600 μ l (7 samples, 800 μ l per sample) of blood is obtained (Table 5). Blood samples will be collected in 800 μ L aliquots. Children who have only 1 evaluable PK sample will be included in the analysis, but additional participants may be enrolled to ensure at least 100 children with < 4 adequate PK samples.

Table 5. PK/PD/Biomarker samplin

Sample Number	Per Patient Prioritization	Time	Per patient blood collection
1	Please always try to collect this	Pre-dose (biomarker only)	$4 \ge 200 \text{ uL} = 800 \text{ uL}$
2		0-30 minutes after the start of CPB	
3	Collect a minimum of 2 of any	0-30 minutes after MUF	
4	of these 5 time points to collect	1-2 hours after completion of CPB	4 x 200 uL = 800 uL
5	a minimum total of 3 time	4-6 hours after completion of CPB	$4 \ge 200 \text{ uL} = 800 \text{ uL}$
6	points per participant.	16-24 hours after completion of CPB	
7	If participating in the biomarker arm, then please always try to collect this	36-48 hours after completion of CPB	4x 200 uL = 800 uL

Timed PK/PD/Biomarker sample handling procedures (plasma):

Assays to measure methylprednisolone concentrations and measures of the inflammatory response to CPB in plasma will be conducted at a central lab using validated bioanalytical assays. The date and time will be recorded for the administration of study drug/placebo, and the acquisition time of the PK sample.

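### Methylprednisolone CL and Vd rest on non-compartmental analysis although children may have only one or two samples, and the PK top-up target is reversed as printed

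*Combined protocol and SAP*

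**What the plan says.** Pharmacokinetics is among the objectives in the Synopsis. Tmax, Cmax, CL and Vd are listed endpoints there and in section 4.3.2. Section 4.1 describes the PK work as ancillary and limited to select centres.

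The only estimation method for methylprednisolone is one Synopsis sentence: "PK parameters will be estimated by non-compartmental analysis using" WinNonLin. Section 10 adds just the PK population (10.7): methylprednisolone recipients with one or more evaluable samples. Nothing says whether parameters are derived per child or from pooled data, or how many samples a child needs to contribute each parameter.

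Section 6.5 states: "Children who have only 1 evaluable PK sample will be included in the analysis". The same sentence continues that "additional participants may be enrolled to ensure at least 100 children with < 4 adequate PK samples".

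Table 5 has a pre-dose sample marked for biomarkers only, five post-dose windows up to 16–24 h after bypass, and a 36–48 h sample. Sites are to "Collect a minimum of 2 of any" of the five windows, to reach "a minimum total of 3 time" points. The instruction for the 36–48 h sample is: "If participating in the biomarker arm, then please always try to collect this". Under section 4.3.2, parents of "participants may elect to participate in the PK/PD, the Biomarker studies or both", so a PK-only child is possible.

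Population methods appear in two other places. A footnote in section 4.4 refers to a separate population PK study as the basis for sampling times. The single-site sub-study in section 15.6 uses a mixed-effects model on leftover plasma, mainly for acetaminophen. Neither specifies a model for methylprednisolone.

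**The concern.** The inclusion rule and the analysis method do not fit together if the analysis is per child. A child with one sample is in the PK population but cannot yield CL or Vd. A child with two yields them from a line through two points, with no way to judge its fit. Whose estimates are reported, and how reliable they are, would depend on which windows were drawn, with no rule set beforehand. Observed Cmax and Tmax have the same weakness, because they depend on whether an early window was taken.

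The top-up rule should be the safeguard. It follows the allowance for one-sample children with a contrasting clause, so its evident purpose is to secure enough better-sampled children. As printed it does the opposite. What is at stake is the usefulness of a stated PK objective that requires blood draws in infants.

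**Working it through.** **Reproducing the plan's figure.** 7 samples × 800 µL = 5600 µL, which agrees with section 6.5. The target of 100 children comes with no precision or power basis, so there is nothing to reproduce for it.

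**The top-up rule, read literally.** One hundred children with 1, 2 or 3 samples each satisfy it. One hundred children with 4 or 5 each do not.

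**Samples against parameters.** A log-linear terminal slope from n samples has n − 2 residual degrees of freedom: none can be fitted for n = 1, zero remain for n = 2, one for n = 3. Two of five windows can be chosen in 10 ways. Six pairs omit the first window (two chosen from the other four), and by the same count six omit the 16–24 h window.

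**Extrapolated area.** Assume mono-exponential decline, bypass of 1 to 4 h and samples at window midpoints. The share of AUC beyond the last sample is exp(−k × t_last), with k = ln 2 / half-life. With a 2 h bypass and an 18 h half-life, the latest possible sample (22 h) leaves 2^(−22/18) = 43% extrapolated. Across 1 to 4 h bypass at 18 h, all 10 pairs leave more than 20% extrapolated (range 40–95%). At 3 h and 6 h, 3 to 6 of the 10 pairs do.

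**Half-lives used.** 18 h is from section 4.3.3. The package insert (section 15.3) says that excretion is almost finished by 12 h. If that means a fraction f, half-life = 12 × ln 2 / (−ln(1 − f)), which is 3.6 h for f = 0.90 and 1.8 h for f = 0.99. I used 18, 6 and 3 h.

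**Per-child error, by simulation.** Assumptions not in the documents: one compartment, 2 h bypass, modified ultrafiltration (MUF) at the end of bypass, windows drawn at random, 30% between-child variation and 15–25% residual error. There were 200,000 children per scenario, with time zero at dosing (Appendix C). Entries are the percentage of children whose estimate is undefined or more than 2-fold off.

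| Samples | Quantity | 18 h | 6 h | 3 h |
|---|---|---|---|---|
| Two windows | slope | 41–54 | 17–27 | 6–14 |
| Two windows | CL | 36–46 | 11–19 | 4–8 |
| Three windows | slope | 21–35 | 4–11 | 1–3 |
| Three windows | CL | 18–29 | 3–7 | 0.4–2 |
| Two windows plus 36–48 h | slope | 0.2–2 | about 0 | about 0 |
| Two windows plus 36–48 h | CL | under 1 | under 1 | under 1 |

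The three designs are the possible readings of the third time point: pre-dose (so two PK samples), a third window, or the late sample.

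**Typical CL at trial level.** Two windows per child, a quarter of children reduced to one sample. Entries are the percentage of simulated trials with typical CL within a factor of 1.2 of the truth.

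| Method | Recipients | 18 h | 6 h | 3 h |
|---|---|---|---|---|
| Population model | 100 | 95–100 | 99–100 | 99–100 |
| Pooled non-compartmental | 100 | 91–96 | 99–100 | 99–100 |
| Median of per-child estimates | 100 | 37–71 | 97–99 | 97–99 |
| Population model | 50 | 87–92 | 97 | 97–100 |
| Pooled non-compartmental | 50 | 80–86 | 96–97 | 97–98 |

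The population model fitted was the one that generated the data, so its rows are a best case. Fifty recipients is what a target of 100 gives under 1:1 allocation if both arms count (100 × 0.5).

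**The case against.** The strongest reply is that the Synopsis does not say per child. Admitting one-sample children is consistent with pooled non-compartmental analysis, which comes close to the population model for typical CL at 100 recipients. That stands. The per-child error rates do not describe a pooled analysis, and they should not be set against a trial-level quantity as if the two were the same. What remains is that pooling is nowhere stated and does not give between-child variability.

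The third time point in Table 5 may simply be the pre-dose sample plus two windows, and the table's layout may have suffered in extraction. That is fair, and it is a floor: up to six post-dose samples are allowed. The unstated level of analysis, the per-parameter minimum and the third time point are missing detail and would not carry the point alone.

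The inequality may be a symbol lost in PDF reading, and the rule is permissive. So it must be checked against the source. If it is printed this way there, it is a recruitment threshold that counts the wrong children.

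Two practical objections also have force. Amendment 5 suggests that the trial was near its end, so correcting the target may no longer change sampling, although the analysis method can still be settled. And confining the 100 to recipients would mean sampling about 100 / 0.5 = 200 children under masked 1:1 allocation, if the present figure counts both arms.

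**Conclusion.** The point holds in two parts. The top-up target is reversed as printed; that follows from the text with no modelling, subject to a check of the symbol. And the sole named method, applied per child, cannot give CL or Vd for some children the plan admits and gives them without residual degrees of freedom for others, whereas a population model uses every admitted child and gives between-child variability.

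A reader might infer that non-compartmental analysis cannot work here, or that about half the children's clearances will be badly wrong. The documents support neither. Pooling would be workable, and the 36–54% figures arise only with per-child analysis, an 18 h half-life, two samples and no late sample. At 3 h the two-window figures are 4–14%, and with the 36–48 h sample the CL figure is under 1%. Half-life, bypass time and variability are assumed, except that 18 h is the protocol's own value, given to justify the length of adverse-event follow-up. The documents do not say how many children will be near the minimum, so no trial-level error rate can be given. Nor do the sub-study's model or the section 4.4 footnote show that a population analysis of methylprednisolone is already planned.

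The change should be made. It concerns an ancillary subset, and the primary endpoint is unaffected.

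**What to change.** 1. **Section 6.5.** Check the inequality against the source and correct it so that the target counts adequately sampled children. Four or more is the probable intention, but that is an inference for the sponsor to confirm. State whether the 100 counts all sampled children or methylprednisolone recipients only. In the same edit, say which sample is the third for a PK-only child.
2. **Synopsis, with section 4.3.2 matched to it.** Estimate CL and Vd with a population (nonlinear mixed-effects) model, using actual times since dose in the section 10.7 PK population, and report between-child variability and precision. Keep Cmax and Tmax as endpoints, but report them, and any per-child non-compartmental estimates, only for children meeting a minimum number and spread of samples set before the data are seen.

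If the sponsor prefers to keep non-compartmental analysis, the least that is needed is to state whether it is pooled or per child and the minimum data for each parameter.

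Cost: wording, plus methylprednisolone modelling that the single-site sub-study does not cover. No samples beyond the cap of seven are required. If a target of four or more is confirmed while enrolment is open, some children would be sampled above the present minimum. Counting recipients only could roughly double the number of children sampled, which is why that choice is left to the sponsor.

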3 BACKGROUND INFORMATION

3.1 Summary of Experience in the Perioperative Setting in Children with CHD

Some surgeons/centers currently administer perioperative high dose (20mg to 60mg) intravenous methylprednisolone before pediatric heart surgery with CPB. In a national registry study of > 3000 neonates with data capture spanning 2004 to 2008, 62% of neonates undergoing surgery with CPB received perioperative methylprednisolone while 38% did not. Of those receiving methylprednisolone, 22% received methylprednisolone on both the day before, and day of surgery, 12% on the day before surgery only, and 28% on the day of surgery only. In a 2nd national registry study including > 25,000 infants undergoing CPB operations (2003-2008), 57% received perioperative corticosteroids while 43% did not.[21] Results of a survey of surgeons from the Congenital Heart Surgeon's Society were similar; 28% did not routinely use steroids for neonatal heart surgery. Of the 72% that did routinely use steroids, ~1/3rd administered steroids pre-operatively and intra-operatively and the remainder gave intra-operative steroids only.[22]

Several previous small translationally focused clinical trials have evaluated the safety and efficacy of methylprednisolone. In the largest contemporary trial, neonates scheduled for cardiac surgery were prospectively randomized to receive either 2-dose (8 hours preoperatively and operatively, n = 39) or single-dose (operatively, n = 37) methylprednisolone at 30 mg/kg IV per dose in a prospective double-blind trial. Neonates receiving pre-operative methylprednisolone therapy demonstrated significantly reduced pre-operative pro-inflammatory cytokines including interleukin-6 and 8. There were no differences between the two groups in post-operative pro-inflammatory markers and no differences in the incidence of post-operative low cardiac output syndrome. [13, 14] Methylprednisolone was well tolerated with no adverse drug reactions. The overall incidence of post-operative infection was 13% (10/76) and 4% (3/76) received a post-operative insulin infusion for hyperglycemia.

A meta-analysis evaluated six previous steroid trials in children undergoing heart surgery with CPB. The combined enrollment of these six trials was 232 participants including 116 receiving peri-operative steroids; two of these studies used methylprednisolone at doses of 30mg/kg IV per dose (n=67 patients). The results of this meta-analysis demonstrated a nonsignificant trend of reduced mortality in steroid-treated patients (11 [4.7%] vs 4 [1.7%] patients; odds ratio, 0.41; 95% CI, 0.14–1.15; p = 0.089). Steroids had no effects on mechanical ventilation time (117.4 \pm 95.9 hr vs 137.3 \pm 102.4 hr; p = 0.43) and ICU length of stay (9.6 \pm 4.6 d vs 9.9 \pm 5.9 d; p = 0.8). Perioperative steroid administration reduced the prevalence of renal dysfunction (13 [54.2%] vs 2 [8%] patients; odds ratio, 0.07; 95% CI, 0.01–0.38; p = 0.002). There were no significant differences in the adverse event profiles for patients receiving steroids versus placebo.[20]

The conclusions of the aforementioned studies, as well as several associated editorials have all been that a large, randomized, controlled trial is needed to evaluate the safety and efficacy of perioperative steroids for infant heart surgery with CPB.[13, 14, 16, 20]

